#### **14.1 Protocol amendments**

Any change or addition to the protocol can only be made in a written protocol amendment that must be approved by Novartis, health authorities where required, and the IRB/IEC prior to implementation.

Only amendments that are required for participant safety may be implemented immediately provided the health authorities are subsequently notified by protocol amendment and the reviewing IRB/IEC is notified.

Notwithstanding the need for approval of formal protocol amendments, the investigator is expected to take any immediate action required for the safety of any participant included in this study, even if this action represents a deviation from the protocol. In such cases, Novartis should be notified of this action and the IRB/IEC at the study site should be informed according to local regulations.

## 16 Appendices

### 16.1 Appendix 1: Clinically notable laboratory values and vital signs

The following specific criteria have been identified for this study. Should these criteria be met, a re-test must be done within 5 days after the first assessment. Discontinuation of the study treatment should be considered if the abnormal hematology parameter is confirmed:

- Hemoglobin: < 10 g/dl
- Platelets: < 75 000/mm^3
- Leukocytes: < 3 000/mm^3
- Neutrophils: < 1 500/mm^3

For all other laboratory assessments, the central laboratory will flag laboratory values falling outside of the normal ranges on the central laboratory report (which the investigator should review and sign-off) and the investigator will report any values considered clinically significant in the eCRF.

Refer to [Section 16.2](#) for clinically notable laboratory values for hepatotoxicity.

Refer to [Section 16.3](#) for clinically notable laboratory values for nephrotoxicity.

For ECGs, a notable QTc value is defined as a QTc (Fridericia's) interval of greater than 450 msec for males or greater than 460 msec for females – all such ECGs will be flagged by the central CRO's cardiologist and require assessment for clinical relevance by the investigator. Confirmed QTcF > 500 msec requires discontinuation of study treatment.

#### 16.1.1 Guidance on monitoring infections

All infections that develop during the study will be reported as AEs on the respective AE eCRF pages. Treatment and additional evaluations (e.g. WBC/Lymphocyte) or other needed investigations / assessments to monitor for signs and symptoms of infection will be performed at the discretion of the Investigator.

The Investigator should remind the participant of the risk of infections and instruct them to promptly report any symptoms of infections to the Investigator. The participants must also be reminded to always carry their Participant Information Card (with site contact information and which identifies them as participants in a clinical study with investigational and control agents with potential immunosuppressive effects) and to show this to any local healthcare provider they may consult and ask that the Investigator be contacted.

In the case of suspected or confirmed serious or atypical infection, study drug interruption should be considered. The Investigator should inform the Sponsor of any such cases.

When evaluating a participant with a suspected infection, the most sensitive tests available should be used (i.e. that directly detect the pathogen, as with PCR).

The Investigator should consider early treatment with specific antimicrobial therapy on the basis of clinical diagnosis or suspicion thereof in consultation with infectious disease experts, as appropriate. The Investigator should inform the Sponsor of any such cases.

### **16.1.2 Guidance on immunizations**

Administration of live or live-attenuated vaccines (including live or live-attenuated SARS-CoV-2 (COVID-19)) should be avoided 6 weeks before and during treatment with remibrutinib and for 4 weeks after the last study drug dose. Further, participants are encouraged to perform necessary last dose of **non-live** vaccines (including for COVID-19) at least 4 weeks before randomization, if available, and according to local practice.

The safety of and ability to generate a primary or anamnestic response to immunization with live, live-attenuated, or inactivated vaccines during remibrutinib treatment has not been investigated. The response to vaccination (including non-live vaccines) could be impaired when B-cells are inhibited.

It is recommended that the Investigator review the participant's immunization history as part of the initial screening procedure for a participant being considered for treatment with remibrutinib.

Vaccination of the participant (including COVID-19 vaccine), in compliance with local area vaccination guidelines for the patient population being treated, is recommended prior to administration of remibrutinib.

## 16.2 Appendix 2: Liver event and laboratory trigger definitions & follow-up requirements

**Table 16-1 Liver event and laboratory trigger definitions**

	Definition/ threshold

Liver laboratory triggers
 
If ALT, AST and total bilirubin normal at baseline:
	
 
ALT or AST > 5 × ULN
 
ALP > 2 × ULN (in the absence of known bone pathology)
 
Total bilirubin > 3 × ULN (in the absence of known Gilbert syndrome)
 
ALT or AST > 3 × ULN and INR > 1.5
 
Potential Hy's Law* cases (defined as ALT or AST > 3 × ULN and Total bilirubin > 2 × ULN [mainly conjugated fraction] without notable increase in ALP to > 2 × ULN)
 
Any clinical event of jaundice (or equivalent term)
 
ALT or AST > 3 × ULN accompanied by (general) malaise, fatigue, abdominal pain, nausea, or vomiting, or rash with eosinophilia
 
Any adverse event potentially indicative of a liver toxicity
 

If ALT or AST abnormal at baseline:	
 
ALT or AST > 3x baseline AND > 5 x ULN
 

\*Treatment-emergent elevations in AST or ALT (>3x ULN or increase of >3x above baseline visit levels, if >ULN at baseline) in combination with total bilirubin >2x ULN (or >2x above baseline visit levels, if >ULN at baseline visit) or jaundice in the absence of cholestasis (defined as ALP < 2 ULN) or other causes of hyperbilirubinemia can be an indicator of severe drug induced liver injury (Hy's Law). For this reason, a potential Hy's Law case requires expedited reporting, and will be handled as a serious unexpected adverse event (assessing it as medically significant in the absence of any other seriousness criteria). It must be reported as an SAE to the sponsor promptly (i.e., even before all other possible causes of liver injury have been excluded). Reporting should include all available information, especially that needed for evaluating the diagnosis, severity and likelihood that the study treatment caused the reaction. For patient monitoring and to better understand potential etiologies, the investigator must initiate a close follow-up until complete resolution of the problem and completion of all attempts to obtain supplementary data.

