20. Patients with history of splenectomy.
21. Known or suspected ongoing, chronic or recurrent infectious disease including but not limited to tuberculosis, atypical mycobacterioses, listeriosis, aspergillosis, or endemic mycoses, and/or known positivity for human immunodeficiency virus (HIV) infection. HIV antibody tests will be performed to determine HIV status with follow-up testing/reporting as required by local regulation.

22. Active systemic bacterial, viral, parasitic or fungal infection that are, in the opinion of the investigator, clinically significant, including but not limited to infections requiring hospitalization or IV antibiotics.
23. Evidence of an ongoing hepatitis C infection (e.g. defined by the detection of hepatitis C ribonucleic acid (HCV-RNA) at screening) and/or an ongoing hepatitis B infection (defined by the detection of hepatitis B virus surface antigen (HBsAg) and/or hepatitis B virus (HBV)-DNA at screening; participants who are positive for anti-hepatitis B core (HBc) antibodies but who are negative for antibodies against HBsAg and HBV-DNA can be included into the study if they agree to monitoring for HBsAg and HBV-DNA reactivation).
24. Active, chronic disease of the immune system (including stable disease treated with immune therapy, e.g. rheumatoid arthritis, systemic lupus erythematosus, etc.) with the exception of well-controlled diabetes or thyroid disorder.
25. History or current hepatic disease including but not limited to acute or chronic hepatitis, cirrhosis or hepatic failure or aspartate aminotransferase (AST)/ alanine aminotransferase (ALT) levels of more than 1.5 x upper limit of normal (ULN) or International Normalized Ratio (INR) of more than 1.5 at screening.
26. History of renal disease, creatinine level above 1.5x ULN, or estimated Glomerular Filtration Rate (eGFR) <45ml/min (using the Cockcroft-Gault equation) at screening.
27. History or evidence of ongoing alcohol or drug abuse, within the last 6 months prior to screening.
28. Pregnant or nursing (lactating) females.
29. Women of childbearing potential, defined as all women physiologically capable of becoming pregnant, unless they are using highly effective methods of contraception while taking study treatment and for at least 2 weeks after stopping study medication.  
Highly effective contraception methods include:

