## **9 Discontinuation and completion**

### **9.1 Discontinuation from study treatment and from study**

#### **9.1.1 Discontinuation from study treatment**

Discontinuation of study treatment for a participant occurs when study treatment is stopped earlier than the protocol planned duration and can be initiated by either the participant or the investigator. The investigator must discontinue study treatment for a given participant if he/she believes that continuation would negatively impact the participant's well-being.

Study treatment must be discontinued under the following circumstances:

- Participant decision
- Pregnancy
- Any SAE, with the exception of anaphylaxis unrelated to study drug, and which does not require hospital admission for  $\geq 24$  hours.
- Any severe AE that is assessed to be at least possibly related to study drug
- Any moderate to severe infection
- Participant requires use of prohibited treatment as per [Section 6.2.2](#)
- Participant failure to comply with the study protocol results in potential risk to the participant
- Participant experiences a moderate or severe hypersensitivity event unrelated to the DBPCFC and suspected to be related to study treatment
- Confirmed QTcF  $> 500$  msec
- Abnormal liver laboratory results requiring discontinuation (see [Section 16.2](#))
- Abnormal renal laboratory results requiring discontinuation (see [Section 16.3](#))
- Platelets  $< 75,000/\text{mm}^3$
- Clinically significant spontaneous bleeding events
- Any other adverse event or laboratory abnormality that in the judgment of the investigator prevents the participant from safely continuing in the study
- Any protocol deviation or other situation that results in a significant risk to the participant's safety

If discontinuation of study treatment occurs, the investigator should make a reasonable effort to understand the primary reason for the participant's premature discontinuation of study treatment and record this information. If treatment code has been broken as noted in [Section 6.5](#) and [Section 6.7.3](#), and site personnel and sponsor determine discontinuation of study treatment is indicated, this information should be recorded. The investigator must also contact the IRT to register the participant's discontinuation from study treatment.

**All participants who discontinue from study treatment prematurely should complete the End of Study visit at the time of treatment discontinuation.**

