**Table 16-2 Follow up requirements for liver laboratory triggers - ALT, AST, TBL**

	ALT	TBL	Liver Symptoms	Action
ALT increase without bilirubin increase:				
	If normal at baseline: ALT > 5 x ULN for more than two weeks OR ALT > 8 x ULN If elevated at baseline: ALT > 3 x baseline AND > 5 x ULN for more than two weeks OR ALT ≥ 5 x baseline AND ≥ 8 x ULN	Normal For participants with Gilbert's syndrome: No change in baseline TBL	None	

● Interrupt study treatment

● Measure ALT, AST, ALP, GGT, TBIL, INR, albumin and CK in 48-72 hours.

● Follow-up for symptoms.

● Initiate close monitoring and workup for competing etiologies.

● Study treatment can be restarted if liver enzymes return to baseline.

ALT increase with bilirubin increase:				
	If normal at baseline: ALT > 3 x ULN If elevated at baseline: ALT > 2 x baseline AND > 3 x ULN	TBL > 2 x ULN (or INR > 1.5) For participants with Gilbert's syndrome: Doubling of direct bilirubin	None	
	If normal at baseline: ALT > 3 x ULN If elevated at baseline: ALT > 2 x baseline AND > 3 x ULN	Normal or elevated*	Severe fatigue, nausea, vomiting, right upper quadrant pain*	

\* This situation suggests liver injury based on (i) elevation of ALT, and (ii) the presence of symptoms of liver injury. Even if bilirubin is normal, the presence of liver symptoms indicates potentially severe liver injury.

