**Table 2-4**      **Liver enzyme abnormalities**

Parameter	Criterion
ALT	>3xULN; >5xULN; >8xULN; >10xULN, >20xULN
ALT or AST	>3xULN; >5xULN; >8xULN >10xULN; >20xULN
TBL	>1xULN; >1.5xULN; >2xULN; >3xULN
ALP	>1.5xULN; >2xULN; >5xULN
(ALT or AST) & TBL	>3xULN & (TBL>1.5xULN; >2xULN)
(ALT or AST) & INR	>3xULN & INR>1.5
ALP & TBL	>3xULN; >5xULN & TBL>2xUL
(ALT or AST) & TBL & ALP	ALT or AST>3xULN & TBL >2xULN & ALP <2xULN (Potential Hy's Law).

Similarly, participants meeting specific renal alert criteria at any post-baseline will be summarized according to [Table 2-5](#).

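### Table 16-1's two baseline rows omit raised bilirubin with normal ALT and AST, and when ALT or AST is raised at baseline the table, its footnote, Table 16-2 and SAP Table 2-4 use different liver limits

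*Protocol*

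**What the plan says.** Section 10.2.1 of the protocol requires follow-up of liver events as defined in Table 16-1 and points to Tables 16-2 and 16-3 for further actions.

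- **Table 16-1, first row** ("If ALT, AST and total bilirubin normal at baseline"): eight triggers. They cover ALT or AST alone, ALP, bilirubin, ALT or AST with INR, potential Hy's law, jaundice, ALT or AST with symptoms, and any adverse event suggesting liver toxicity.
- **Table 16-1, second row** ("If ALT or AST abnormal at baseline"): one trigger, ALT or AST above both 3 times baseline and 5xULN.
- **Footnote to the Hy's law bullet**: ALT or AST above 3xULN or "increase of >3x above baseline visit levels, if >ULN at baseline". This is combined with a bilirubin limit of the same form (2xULN, or 2 times a raised baseline) or jaundice, and ALP below 2xULN. A case must be reported promptly as an SAE.
- **Table 16-2**, if ALT is elevated at baseline: "ALT > 2 x baseline AND > 3 x ULN", with bilirubin above 2xULN or INR above 1.5. The table title names ALT, AST and bilirubin.
- **SAP Table 2-4**, potential Hy's law: "ALT or AST>3xULN & TBL >2xULN & ALP <2xULN". Under SAP Section 2.7.3 a case counts as new if the criterion was not met (or was missing) at baseline and is met afterwards.
- **Exclusion criterion 25**: bars ALT or AST above 1.5xULN and INR above 1.5. It gives no bilirubin limit.

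SAP Section 5.2 refers to protocol Section 16.2 for notable liver values, and SAP Section 4 declares no change from the protocol's analyses.

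**The concern.** Three things do not fit together.

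1. The two rows of Table 16-1 do not cover every baseline pattern that the trial can enrol. Raised bilirubin with normal ALT and AST belongs to neither row. The protocol plainly expects such participants, because Tables 16-1 to 16-3 all mention Gilbert's syndrome.
2. For a participant whose ALT or AST is raised at baseline, the trigger row, the reporting footnote, the action table and the SAP count use different limits on the same laboratory values.
3. Table 16-1 can be triggered by AST, but no row of Table 16-2 can be.

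At stake is whether a possible drug-induced liver injury is recognised as a trigger, falls under the mandatory SAE rule, is acted on and is tabulated, all by one consistent definition. Such cases are rare, but finding them is the purpose of these tables.

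**Working it through.** No sample size, power or alpha figure is involved. The check applies each rule to the same values, in multiples of ULN. The worked values are illustrative, and the baselines satisfy criterion 25.

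**1. ALT raised at baseline.** Let b be baseline ALT, with 1.0 < b ≤ 1.5. The on-treatment ALT that must be exceeded is:

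| Place | Formula | Result (xULN) |
|---|---|---|
| Table 16-1, second row | max(3b, 5); 3b is at most 4.5 | 5 |
| Footnote, if the baseline limit replaces the ULN limit | 3b | 3.0 to 4.5 |
| Footnote, if either limit suffices | min(3, 3b) | 3 |
| Table 16-2 (with bilirubin above 2xULN) | max(2b, 3); 2b is at most 3.0 | 3 |
| SAP Table 2-4 | none | 3 |

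If either limit suffices, the footnote agrees with Table 16-2 and the SAP on ALT, and only the Table 16-1 row stands apart. If the baseline limit replaces the ULN limit, there are three different levels.

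**2. Worked case.** Baseline ALT 1.4 with normal bilirubin; on treatment ALT 4.0, bilirubin 2.5, ALP 1.2.

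- Table 16-1, first row: does not apply, because baseline ALT is raised.
- Table 16-1, second row: needs more than 3 × 1.4 = 4.2 and more than 5. Not met.
- Footnote, baseline limit replaces: 4.0 / 1.4 = 2.86, below 3. Not met.
- Footnote, either limit suffices: 4.0 > 3, 2.5 > 2, 1.2 < 2. Met, so a mandatory SAE report.
- Table 16-2: 4.0 > 2 × 1.4 = 2.8, 4.0 > 3, 2.5 > 2. Met.
- SAP Table 2-4: met, and newly occurring. Counted as potential Hy's law.

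**3. Bilirubin alone raised at baseline.** Baseline bilirubin 1.5 and ALT 0.8, no Gilbert's syndrome; on treatment ALT 4.0, bilirubin 2.5, ALP 1.0.

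- Table 16-1: neither row applies.
- Footnote: if the baseline limit replaces, bilirubin must exceed 2 × 1.5 = 3.0, so not met. If either limit suffices, met.
- Table 16-2: met.
- SAP: counted.

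**4. AST.** Take all tests normal at baseline, then AST above 5xULN with normal ALT. The first row of Table 16-1 is triggered. Every row of Table 16-2 sets a condition on ALT, so none is met. The general actions in Section 10.2.1 still apply: repeat tests, close observation, and interruption or discontinuation if appropriate.

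**5. All three tests normal at baseline.** The limits are 3xULN for ALT and 2xULN for bilirubin in all four places. Over a grid of 10,450 on-treatment combinations of ALT, bilirubin and ALP (ALP 1.0 or 1.5), the Hy's law bullet, the footnote, the bilirubin row of Table 16-2 and the SAP disagreed in 0. The grid did not vary conjugated fraction, jaundice, symptoms or INR. Minor differences remain. ALP of exactly 2.0xULN satisfies the bullet but not the footnote or the SAP, and Table 16-2 has no ALP condition. Only the bullet asks for mainly conjugated bilirubin, and only the footnote allows jaundice in place of the bilirubin limit.

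**The case against.** The strongest reply is that these passages serve different purposes. A trigger, an SAE rule, an interruption rule and a descriptive table may have different cut-offs. Table 16-2 never names Hy's law, and acting more widely than the SAE rule is cautious. This stands in part: a lower action limit is not in itself a contradiction. It does not explain why rows that govern follow-up leave out an enrollable baseline, or why the SAP's count carries the Hy's law label with no baseline adjustment while claiming no change from the protocol.

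The second row of Table 16-1 could also be read as adjusting only the 5xULN bullet, with the other triggers meant for everyone. That is possible, but the layout places them under the all-normal label.

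Three stronger readings are tempting and are not supported:

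- A reader might infer that a participant with raised bilirubin alone has no liver safeguard at all. The footnote gives a rule for raised baseline bilirubin, Table 16-2 has a Gilbert's syndrome provision, and Table 16-3 acts on isolated bilirubin and on any adverse event suggesting liver toxicity. The gap is in the rows of Table 16-1.
- A reader might infer that the worked case goes unreported while the SAP counts it. That holds only if the footnote's baseline limit replaces the ULN limit. Even then, the investigator can report it on judgement as medically significant.
- A reader might set "Study treatment can be restarted if liver enzymes return to baseline" in Table 16-2 against Section 9.1.1, which requires stopping for "Any SAE, with the exception of anaphylaxis unrelated to study drug". In the available text the restart wording sits beside the row for ALT rise without bilirubin rise, and the other action cells are blank. Unless the original table shows one merged action cell, no conflict is established.

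**Conclusion.** The point holds as a wording defect. Table 16-1's baseline rows are not exhaustive. For baseline ALT above 1.0 and up to 1.5xULN, the relevant ALT level is 5xULN in the row and 3xULN in Table 16-2 and the SAP. The footnote's level is unsettled: 3xULN, or 3.0 to 4.5xULN depending on baseline. AST-led triggers have no row in Table 16-2, only the general actions of Section 10.2.1.

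The scope is narrow. The ALT and bilirubin differences arise only when ALT, AST or bilirubin is raised at baseline. The documents do not say how many of the 72 participants that would be, so no count is given here, but few are likely to be affected. A reader might also infer an effect on the primary analysis, since stopping or interrupting drug can decide who reaches the final challenge. Nothing in the documents lets that be sized. The case for correction is that a liver safety definition should give one answer for one set of values, and that the correction is cheap.

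**What to change.** Reconcile Table 16-1, its footnote, Table 16-2 and SAP Table 2-4 so that:

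- every enrollable baseline pattern falls in a defined row of Table 16-1;
- the 'or' in the footnote has one stated meaning, for ALT and AST and for bilirubin;
- the role of AST in Table 16-2 is stated;
- the SAP's potential Hy's law count matches the protocol's definition, with plain ULN multiples kept as additional rows if wanted.

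Check the original layout of the action column in Table 16-2 at the same time. The sponsor's hepatic safety group decides which thresholds and triggers apply in each row; none is proposed here.

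The cost is wording in one appendix table, its footnote and the action table, plus one SAP definition. No extra visit, sample or participant is needed.

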**Table 16-2 Follow up requirements for liver laboratory triggers - ALT, AST, TBL**

	ALT	TBL	Liver Symptoms	Action
ALT increase without bilirubin increase:				
	If normal at baseline: ALT > 5 x ULN for more than two weeks OR ALT > 8 x ULN If elevated at baseline: ALT > 3 x baseline AND > 5 x ULN for more than two weeks OR ALT ≥ 5 x baseline AND ≥ 8 x ULN	Normal For participants with Gilbert's syndrome: No change in baseline TBL	None	

● Interrupt study treatment

● Measure ALT, AST, ALP, GGT, TBIL, INR, albumin and CK in 48-72 hours.

● Follow-up for symptoms.

● Initiate close monitoring and workup for competing etiologies.

● Study treatment can be restarted if liver enzymes return to baseline.

ALT increase with bilirubin increase:				
	If normal at baseline: ALT > 3 x ULN If elevated at baseline: ALT > 2 x baseline AND > 3 x ULN	TBL > 2 x ULN (or INR > 1.5) For participants with Gilbert's syndrome: Doubling of direct bilirubin	None	
	If normal at baseline: ALT > 3 x ULN If elevated at baseline: ALT > 2 x baseline AND > 3 x ULN	Normal or elevated*	Severe fatigue, nausea, vomiting, right upper quadrant pain*	

\* This situation suggests liver injury based on (i) elevation of ALT, and (ii) the presence of symptoms of liver injury. Even if bilirubin is normal, the presence of liver symptoms indicates potentially severe liver injury.

